### 3.4 Inclusion criteria

- (1) Diagnosis of NEC and having undergone surgical treatment, confirmed by clinical manifestations (e.g., abdominal distension, bloody stools), radiological evidence (pneumatosis intestinalis, portal venous gas, or pneumoperitoneum), and pathological examination in accordance with established guidelines;
- (2) Availability of complete medical records for data extraction.

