## Abstract

Object name	Analysis of integrated clinical, laboratory and prognostic data of neonates with necrotizing enterocolitis
Goal of study	This retrospective cohort study aims to enroll patients with necrotizing enterocolitis (NEC) from July 1, 2017 to December 31, 2022, conduct a comprehensive analysis of their clinical characteristics, metabolic indicators, laboratory parameters, prognosis, and outcomes, and identify indicators that may predict the progression of neonatal NEC and its associated mortality.
Research design	Retrospective cohort study
Research period	July 1, 2024 to June 30, 2025
Leading unit	Guangzhou Women and Children's Medical Center
Research Consultant	[name]; [name]
Research object	Neonates with necrotizing enterocolitis (NEC) from July 1, 2017 to December 31, 2022, conduct a comprehensive analysis of their clinical characteristics, metabolic indicators, laboratory parameters, prognosis, and outcomes.
Inclusion criteria	(1) Diagnosis of NEC
Excluded criteria	Data that meets any of the following conditions need to be eliminated: (1) Congenital gastrointestinal malformations (e.g., intestinal atresia, Hirschsprung's disease) or spontaneous intestinal perforation; (2) Hereditary metabolic disorders; (3) refusal of participation.
Sample size	220 newborns who suffered from necrotizing enterocolitis between

	July 1, 2017 to December 31, 2022
Data collection	Data collection was performed via structured extraction from electronic medical records. The following variables were systematically retrieved: (1) Neonatal medical history, including sex, gestational age, birth weight, and history of birth asphyxia (e.g., Apgar scores); (2) Maternal medical history, particularly mode of delivery, chorioamnionitis, and premature rupture of membranes; (3) NEC-related clinical parameters: Bell's staging, clinical manifestations (abdominal distension, bloody stools, pneumoperitoneum), complications (patent ductus arteriosus [PDA], sepsis, shock), therapeutic interventions (mechanical ventilation, surgical treatment), and mortality; (4) CBC parameters, lactate levels, and parameters required for calculating the nSOFA score at the onset of NEC.

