## 1. project basis

### 1.1 Research background

Necrotizing enterocolitis (NEC), a life-threatening gastrointestinal disorder predominantly, affects 5–12% of very low birth weight (VLBW) neonates, with 20–40% of cases progressing to severe disease requiring surgical intervention, while survivors often endure lifelong consequences, including short-bowel syndrome and neurodevelopmental impairments [1-4]. Despite advances in neonatal care, early identification of high-risk patients remains challenging due to the nonspecificity of clinical signs (e.g., abdominal distension, feeding intolerance) and radiographic findings (e.g., pneumatosis intestinalis), which frequently manifest only after irreversible bowel damage has occurred [5]. Furthermore, current diagnostic tools or conventional biomarkers lack both sensitivity and specificity for early risk stratification of NEC, underscoring an urgent need for biomarkers that integrate pathophysiological mechanisms to guide preemptive therapeutic strategies.

Emerging evidence underscores the multifactorial pathophysiology of NEC, where intestinal ischemia-reperfusion injury, exaggerated immune activation, and microbial dysbiosis converge to drive disease progression [6]. Hypoxic-ischemic injury constitutes a key pathological mechanism underlying intestinal mucosal damage in NEC, driving dysregulation of cellular processes including apoptosis, autophagy, proliferation, and migration within intestinal tissues [7]. In infants with NEC, persistent hypoxemia and compromised tissue perfusion induce metabolic reprogramming, marked by a shift toward glycolytic dominance—a compensatory adaptation to oxygen deprivation. Within this framework, serum lactate, as a well-established marker of tissue hypoperfusion and anaerobic metabolism, has garnered attention for its prognostic relevance. Elevated lactate levels correlate with transmural intestinal necrosis and predict fatal outcomes in NEC, reflecting the severity of ischemic insult [8,9]. However, lactate alone lacks specificity, as hyperlactatemia may arise from concurrent sepsis or perinatal asphyxia, limiting its standalone utility [10,11]. Recent studies propose combining lactate with

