immune-inflammatory biomarkers (such as intestinal fatty acid binding protein or albumin) to address this limitation [12,13]. Peripheral blood cell analysis serves as a widely accessible and rapid auxiliary diagnostic tool in neonatal intensive care units (NICUs). Dynamic changes in peripheral white blood cell (WBC) counts and subset distribution have been validated as biomarkers closely associated with NEC [14]. Accumulating evidence underscores the involvement of lactate metabolism in immunomodulation and its influence on disease pathogenesis [15]. However, the combined utility of lactate levels and peripheral WBC profiles for NEC diagnosis and prognostic stratification remains unexplored.

As NEC progresses, particularly in cases of perforated NEC, it can evolve from a localized intestinal disease into a systemic illness characterized by a sepsis-like state and multi-organ dysfunction. The Neonatal Sequential Organ Failure Assessment (nSOFA) score is a validated tool designed to objectively quantify the degree of organ dysfunction in critically ill neonates by evaluating the respiratory, cardiovascular, and hematologic systems [16]. Studies have demonstrated that higher nSOFA scores are strongly and independently associated with mortality risk in neonates with respiratory distress syndrome, late-onset sepsis, and NEC [16-18]. However, single nSOFA lacks sufficient sensitivity for severe NEC subtypes like PNEC-specific risk stratification: while it predicts overall NEC mortality and the need for surgical intervention [16], existing studies have not specifically evaluated its performance in distinguishing NEC from non-perforated NEC or predicting PNEC-related mortality. The Lewis et al. [16] study included surgical NEC (e.g., laparotomy or peritoneal drain placement) but did not isolate PNEC as a distinct endpoint, leaving a critical gap in understanding how nSOFA performs in this highest-risk subgroup.

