## 2. Research objective

This retrospective cohort study aims to enroll patients with necrotizing enterocolitis (NEC) from July 1, 2017 to December 31, 2022, conduct a comprehensive analysis of their clinical characteristics, metabolic indicators, laboratory parameters, prognosis, and outcomes, and identify indicators that may predict the progression of neonatal NEC and its associated mortality.

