## 3. Research scheme and technical route

### 3.1 Research Design

The principal investigator (PI) and project leader of this study are [name], chief physician of pediatrics of the Guangzhou Women and Children's Medical Center. In this study, a retrospective analysis was conducted on 220 enrolled neonates with necrotizing enterocolitis (NEC), with data collected from July 1, 2017 to December 31, 2022. Statistical methods including correlation analysis, multivariate logistic regression, mediation analysis, and receiver operating characteristic (ROC) curve analysis were employed to perform mutual analysis of the collected clinical data, laboratory parameters, and prognostic/mortality outcomes. This analysis aimed to identify meaningful biomarkers and establish a predictive model, thereby providing evidence for the pathophysiological mechanisms underlying NEC progression. It is anticipated that this will optimize clinical decision-making for NEC patients and improve the survival rate and quality of life of these neonates.

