### 3.2 Sample size

220 newborns who suffered from necrotizing enterocolitis between July 1, 2017 to December 31, 2022.

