### 3.3 data collection

Data collection was performed via structured extraction from electronic medical

records. The following variables were systematically retrieved: (1) Neonatal medical history, including sex, gestational age, birth weight, and history of birth asphyxia (e.g., Apgar scores); (2) Maternal medical history, particularly mode of delivery, chorioamnionitis, and premature rupture of membranes; (3) NEC-related clinical parameters: Bell's staging, clinical manifestations (abdominal distension, bloody stools, pneumoperitoneum), complications (patent ductus arteriosus [PDA], sepsis, shock), therapeutic interventions (mechanical ventilation, surgical treatment), and mortality; (4) CBC parameters, lactate levels, and parameters required for calculating the nSOFA score at the onset of NEC.

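### Section 3.4 admits only operated NEC infants, yet surgical NEC is listed as an outcome and the stated target is neonatal NEC in general

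*Combined protocol and SAP*

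**What the plan says.** Section 3.4(1) sets the entry condition as "Diagnosis of NEC and having undergone surgical treatment, confirmed by clinical manifestations". It goes on to name radiological evidence and pathological examination, joined by an *and*, so all three kinds of evidence are required of an infant who has been operated on.

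The Abstract gives a single inclusion criterion, "1) Diagnosis of NEC", with no surgery or pathology condition. Section 3.2 describes the sample as "220 newborns who suffered from necrotizing enterocolitis between July 1, 2017 to December 31, 2022", and Section 3.1 likewise speaks only of enrolled neonates with NEC.

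Section 3.6 lists four outcomes. Perforated NEC (PNEC) and in-hospital mortality are primary; Bell's staging and surgical NEC are secondary. Surgical NEC is not defined there. The only gloss is in Section 1.1, in a remark on an earlier nSOFA study: "study included surgical NEC (e.g., laparotomy or peritoneal drain placement) but did not isolate PNEC as a distinct endpoint".

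The stated scope is wider than operated infants. The aim in Section 2 is to "identify indicators that may predict the progression of neonatal NEC and its associated mortality". Section 3.1 anticipates that "this will optimize clinical decision-making for NEC patients and improve the survival rate". Section 1.1 motivates the work by saying that existing tools "lack both sensitivity and specificity for early risk stratification of NEC".

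**The concern.** An outcome that is also an entry condition cannot vary within the cohort. If every infant was admitted because of an operation, having had an operation cannot be predicted, compared or discriminated in those data.

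The second issue is the population. Under Section 3.4 the PNEC and mortality results describe infants who reached surgery. An infant who died of NEC without an operation, or who perforated and was not operated on, does not enter the numerator or the denominator. A reader of Sections 2 and 3.1 would take the results as prediction for neonatal NEC in general. Eligibility sets the denominator of every result, so two teams following this document could assemble different cohorts.

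**Working it through.** **Plan's own figure.** The 220 in Section 3.2 is a count over a date range. No power, effect size or event rate is given, so there is no calculation to reproduce. The check is a comparison of sections plus a count.

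**Inputs.** N = 220 (Section 3.2). Entry rule: operated NEC with clinical, radiological and pathological evidence (Section 3.4(1)). Outcomes: 2 primary + 2 secondary = 4 (Section 3.6). Meaning of surgical NEC: laparotomy or drain placement, given as examples (Section 1.1).

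**Step 1: sections side by side.**

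| Place | Surgery required? | Pathology required? |
|---|---|---|
| Abstract, inclusion | not stated | not stated |
| 3.1, 3.2, description of the 220 | not stated | not stated |
| 3.4(1), inclusion | yes | yes |
| 3.6, secondary outcome | treated as something that can vary | – |

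The last two rows conflict whatever view is taken of the Abstract.

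**Step 2: the outcome under Section 3.4.** Two conditions are needed: (A) Section 3.4 selected the 220, and (B) surgical NEC means NEC treated by surgery. With both:

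- infants with the outcome = 220, and comparators = 220 − 220 = 0;
- proportion p = 220/220 = 1, and variance p(1 − p) = 1 × 0 = 0;
- case–comparator pairs available to an AUC = 220 × 0 = 0, and no odds ratio is estimable.

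If either condition fails, these figures do not follow. Without (A), the number operated on is some unreported part of the 220. Without (B), the outcome may vary, but the plan does not say how it is defined.

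**Step 3: outcomes affected.** 1 of 4 overall: 1 of 2 secondary and 0 of 2 primary. Under Section 3.4, PNEC and in-hospital death can still differ between infants, so perforated and non-perforated cases can be compared among those operated on.

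**Step 4: effect on the primary estimates.** This would need counts of operated, unoperated, perforated and deceased infants in the source population. The documents give none, so no size can be computed.

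**The case against.** The strongest reply is that Section 3.4 is the criteria section in the body of the plan and governs, while the Abstract is a shortened summary. The Abstract also omits the complete-records condition of 3.4(2) and the incomplete-data exclusion in 3.5(3), which fits abbreviation better than a rival rule. This largely stands: the Abstract alone would be a minor mismatch. It does not remove the conflict between Sections 3.4 and 3.6, or the gap between Section 3.4 and the scope in Sections 2 and 3.1.

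A second reply is that surgical NEC is undefined and its one gloss describes another study's population. That is fair, and it is why condition (B) is stated. But any other meaning would have to be written into the plan.

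Several stronger readings are tempting and are not supported:

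- *A planned analysis will fail.* Section 3.7 assigns no outcome to any test, regression or ROC curve, and surgical NEC could simply be described. What follows is a constant secondary outcome, not a demonstrated failed analysis.
- *Predictors are measured before it is known who will be operated on.* Section 3.3 gives the timing of "CBC parameters, lactate levels, and parameters required for calculating the nSOFA score at the onset of NEC", but no section gives the timing of surgery or of the decision to operate. Pneumoperitoneum is among the diagnostic findings in 3.4(1), so surgery may already have been foreseen at onset.
- *The number operated on can be inferred from the background.* Section 1.1 gives 20–40% of cases needing surgery, but for very low birth weight infants. The criteria here set no birth-weight limit, so the figure does not size this cohort.

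**Conclusion.** The plan is internally inconsistent about who is in the cohort and should be corrected. On conditions (A) and (B), surgical NEC is 220/220 with no comparators, so one of the two secondary outcomes cannot be predicted or compared. Both primary outcomes remain estimable, but only for operated, pathology-confirmed infants, while the stated target is neonatal NEC without that limit.

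A reader might infer that the primary results are invalid or biased by a known amount. The documents do not support that: a surgery-only cohort is a legitimate object of study, and the difference from an all-NEC cohort cannot be computed from what is given. The defect is a constant outcome and a scope wider than the data, both following from Section 3.4 as written. If the Abstract's criterion was in fact used, neither arises on this ground, but Section 3.4 is then wrong as written.

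**What to change.** State which rule selected the 220 and make the Abstract and Sections 3.1, 3.2, 3.4 and 3.6 agree.

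*If Section 3.4 was used:*

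- add the surgery and pathology conditions to the Abstract and Section 3.2;
- delete surgical NEC as an outcome, or redefine it so that it varies among operated infants;
- restate Sections 1.2, 2 and 3.1 as applying among surgically treated, pathology-confirmed NEC;
- state that unoperated infants, including any who died without surgery, are not represented.

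*If the Abstract's criterion was used:*

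- remove the surgery condition from 3.4(1);
- state how NEC was confirmed in operated and in unoperated infants (the Abstract's silence on pathology is not by itself a reason to delete it);
- define surgical NEC in Section 3.6;
- report how many of the 220 were operated on.

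The cost is mainly wording. Under Section 3.4 it is a narrower stated scope and, unless the outcome is redefined, the loss of one secondary outcome. Under the Abstract's criterion, records may need re-checking against the completeness conditions in 3.4(2) and 3.5(3), which the Abstract omits. The exclusion of malformations and spontaneous perforation is the same in both places, so this conflict gives no reason to re-check it.

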### 3.6 Observation items

- (1). Baseline Characteristics: Neonatal demographics (sex, gestational age, birth weight, small for gestational age [SGA] status), maternal factors (mode of delivery, premature rupture of membranes, chorioamnionitis), neonatal birth history (1-min Apgar score  $\leq 7$ , intrauterine distress), and preterm complications (patent ductus arteriosus [PDA], respiratory distress syndrome [RDS], sepsis, shock), feeding pattern, and requirement for mechanical ventilation.

- (2). Laboratory and Clinical Assessment Indicators: Hepatobiliary function:

Albumin, albumin/globulin ratio, total bile acid; Hematologic and inflammatory parameters: White blood cell (WBC), absolute neutrophil (NEU), lymphocyte (LYM), monocyte (MON), eosinophil (EOS) counts, red blood cell (RBC), platelet (PLT) count, mean platelet volume (MPV), platelet distribution width (PDW), C-reactive protein (CRP), neutrophil-to-lymphocyte ratio (NLR), monocyte-to-lymphocyte ratio (MLR), neutrophil-to-monocyte ratio (NMR), systemic inflammatory index (SII), systemic inflammatory response index (SIRI), aggregate inflammatory systemic index (AISI); Metabolic: Serum lactate, blood glucose; Organ dysfunction assessment: Neonatal Sequential Organ Failure Assessment (nSOFA) score.

(3). Primary Outcome Indicators:

- Occurrence of perforated necrotizing enterocolitis (PNEC);
- In-hospital mortality.

(4). Secondary Outcome Indicators:

- Bell's staging of NEC;
- surgical NEC

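### Section 3.4 admits only infants who had surgery, which follows the onset markers; the Abstract does not, so onset associations with perforation and death may be biased if 3.4 was applied

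*Combined protocol and SAP*

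**What the plan says.** The entry rule differs between parts of the document.

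- Section 3.4, first criterion: "Diagnosis of NEC and having undergone surgical treatment", confirmed by clinical signs, imaging and pathological examination.
- Abstract: the only inclusion item is "1) Diagnosis of NEC".
- Section 3.2: "220 newborns who suffered from necrotizing enterocolitis between July 1, 2017 to December 31, 2022". Section 3.1 likewise describes 220 neonates with NEC. Neither mentions surgery.

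The markers are timed at onset. Section 3.3 collects "CBC parameters, lactate levels, and parameters required for calculating the nSOFA score at the onset of NEC".

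Section 1.1 says of nSOFA: "while it predicts overall NEC mortality and the need for surgical intervention".

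The aim in section 2 is to "identify indicators that may predict the progression of neonatal NEC and its associated mortality", and the Abstract repeats it. Section 1.2 speaks of NEC in preterm infants, and section 3.1 of a predictive model to improve clinical decisions. None of these is limited to operated infants.

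Section 3.6 names two primary outcomes, perforated NEC (PNEC) and in-hospital mortality. Surgical NEC is a secondary outcome. Section 3.7 does not deal with selection into surgery.

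**The concern.** Under section 3.4, entry depends on an event that happens after the predictors are measured. A perforated infant probably enters because of the perforation. A non-perforated infant enters only if the illness led to surgery for another reason. If a marker raises the chance of surgery in non-perforated infants, those in the cohort have higher marker values than non-perforated NEC infants in general. The comparison group is then chosen partly on the marker under test.

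For mortality, infants who die without an operation are left out. What that does to the association depends on which infants they are.

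Two things are at stake. A marker that is useful at onset could look useless, or even protective, for PNEC; section 1.1 gives nSOFA's performance for PNEC as the gap to be filled. And a model built on operated infants cannot be applied at onset, when nobody yet knows who will be operated on. Removing surgical NEC as a secondary outcome (it cannot vary if everyone was operated on) would leave both problems in place.

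**Working it through.** The plan gives no power calculation, event rate or surgery rate by marker or outcome, so there is no figure of its own to reproduce. The check is of direction and possible size. Every surgery rate below is an assumption.

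**1. Exact relation for a binary marker.** Let s(m,y) be the probability of surgery given marker m (1 high, 0 low) and outcome y (1 yes, 0 no). Then

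OR among operated = OR in all NEC × [s(1,1) × s(0,0)] / [s(1,0) × s(0,1)].

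PNEC, true OR 2.0, all perforated infants operated on, so s(1,1) = s(0,1) = 1:

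| Surgery if not perforated, high vs low marker | OR among operated |
|---|---|
| 25% vs 25% | 2.0 × 0.25/0.25 = 2.00 |
| 30% vs 20% | 2.0 × 0.20/0.30 = 1.33 |
| 40% vs 20% | 2.0 × 0.20/0.40 = 1.00 |
| 60% vs 15% | 2.0 × 0.15/0.60 = 0.50 |

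Death, true OR 2.0:

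| Surgery in deaths, high/low | Surgery in survivors, high/low | OR among operated |
|---|---|---|
| 60%/50% | 35%/20% | 2.0 × (0.60×0.20)/(0.35×0.50) = 1.37 |
| 40%/60% | 35%/20% | 2.0 × (0.40×0.20)/(0.35×0.60) = 0.76 |
| 80%/40% | 40%/20% | 2.0 × (0.80×0.20)/(0.40×0.40) = 2.00 |
| 60%/30% | 30%/20% | 2.0 × (0.60×0.20)/(0.30×0.30) = 2.67 |

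For PNEC with near-universal surgery after perforation, the association can only weaken or reverse if the marker raises surgery in the others. For death, every direction is possible.

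**2. Simulation for a continuous marker and PNEC.** Marker x is standard normal; logit P(perforation) = −1.7 + 0.7x (true OR e^0.7 = 2.01, AUC 0.68, perforation about 17.5%). Surgery is 95% if perforated; otherwise logit P(surgery) = −1.4 + g·x. About 33 to 37% are operated on overall.

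| g | Effect on surgery per SD, e^g | OR among operated | AUC | Significant at n = 220 |
|---|---|---|---|---|
| 0 | 1.0 | 2.0 | 0.68 | nearly 100% |
| 0.5 | 1.65 | 1.4 | 0.58–0.59 | about 60% |
| 1.0 | 2.7 | 1.0 | 0.50–0.51 | about 5% |
| 1.5 | 4.5 | 0.8 | 0.45 | 21–24%, wrong direction |

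For comparison, 220 unselected NEC infants detect the marker in about 96% of samples. Ranges cover repeated runs.

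The 95% figure is not essential. If about 80% of perforated infants are operated on at an average marker value, with the same marker slope in both groups, the OR is about 1.5 at g = 0.5 and 1.2 at g = 1.0.

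**3. Simulation for death.** Logit P(death) = −1.1 + 0.8x (OR 2.23, AUC 0.70). If surgery follows logit 0.8x in deaths and −1.2 + 0.3x in survivors, the OR among operated rises to about 2.5 (AUC 0.72). With the slopes exchanged, it falls to about 1.5 (AUC 0.60).

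**4. Scale.** Section 1.1 gives 20–40% needing surgery, in a sentence about very low birth weight infants, so this is for scale only. If the 220 are all NEC, 220 × 0.20 = 44 to 220 × 0.40 = 88 would be operated on. If all 220 were operated on, they come from about 220/0.40 = 550 to 220/0.20 = 1,100 NEC infants.

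**The case against.** A reader might infer that both primary associations are biased towards the null or reversed, and that the mortality AUC is reduced. The documents do not support that. They give no surgery rates by marker or outcome, and there is no bias in the PNEC odds ratio if the marker is unrelated to surgery among non-perforated infants and perforated infants alike. In that case an operated-only sample even detects the marker slightly more often, because about half of it is perforated. A reduced mortality AUC would require, for example, that unoperated deaths are the high-marker infants, which no section says; other patterns raise it.

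Three further objections have force.

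- Support in the text is for nSOFA only. Nothing says that lactate, blood-count indices or albumin predict surgery.
- Bias is relative to a target. Section 1.1 faults an earlier study that included surgical NEC for not isolating PNEC, so perforated versus non-perforated NEC among operated infants can be read as one intended contrast. For that target the estimates are narrow rather than biased. But the aims in the Abstract and sections 1.2, 2 and 3.1 are wider, and the markers are taken at onset.
- It is unclear that the surgery rule was applied at all, because the Abstract and sections 3.1 and 3.2 omit it. Its use is therefore a condition of the conclusion.

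None of this removes the contradiction between entry rules, or the mismatch between an operated-only cohort and a claim about NEC at onset.

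**Conclusion.** The concern holds in conditional form. The firm defect is that section 3.4 requires surgery while the Abstract and sections 3.1 and 3.2 do not, and the aims are stated for NEC without that limit. If section 3.4 was applied, estimates for NEC at onset may be biased:

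- For nSOFA and PNEC, plausibly towards the null or reversed. This rests on two assumptions that the documents do not state: that nearly all perforated infants are operated on, and that nSOFA raises the chance of surgery among the others. Section 1.1 supports the second only in general terms.
- For death, the direction is unknown.
- For the other markers, the same mechanism is an inference.

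The fall from an odds ratio of 2.0 to between 1.4 and 0.8 shows what moderate to strong selection can do. It is not an estimate for this cohort. The matter should be settled before the results are interpreted, because it touches both primary outcomes.

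**What to change.** Establish which rule selected the 220, and reconcile the Abstract and sections 3.1, 3.2 and 3.4 accordingly.

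1. **If selection was on NEC diagnosis alone:** delete the surgery condition from the first criterion in section 3.4. Make pathological examination a confirmation only where tissue exists; left as it is, it would still favour operated infants. Report operated infants as a subgroup. Surgery can still forestall a later perforation in this cohort, so interpretation of PNEC should acknowledge that.
2. **If all 220 were operated on:** restate the primary outcomes in section 3.6 as perforation among infants operated on for NEC, and in-hospital death among operated infants. Drop surgical NEC as an outcome. Limit the predictive claims in the Abstract and sections 1.2, 2 and 3.1 to operated infants. State that a null or inverse PNEC association is not evidence of no predictive value at onset.
3. **Either way:** report how many NEC infants in the window were not operated on, and how many of those died.

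The cost is wording and one count from the same records. The downside is a narrower claim if the cohort is operated-only.

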### 3.5 Excluded criteria

Data that meets any of the following conditions need to be eliminated:

- (1) Congenital gastrointestinal malformations (e.g., intestinal atresia, Hirschsprung's disease) or spontaneous intestinal perforation;
- (2) Hereditary metabolic disorders;
- (3) Incomplete clinical data or refusal of participation.

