### 3.7 Statistical processing

Statistical analyses and graphic visualization were performed using SPSS 26.0 (IBM Corp.) and GraphPad Prism 9.0. Data for normally distributed, skewed distributed, and categorical variables were expressed as mean  $\pm$  standard deviation, median (interquartile range), and frequency (%), respectively. Intergroup comparisons of categorical variables were conducted using the Chi-square ( $\chi^2$ ) test or Fisher's exact test, while continuous variables were analyzed using the Student's t-test or Mann-Whitney U test. Variables with  $p < 0.05$  in univariate analysis were subsequently included in multivariate logistic regression analysis.

Mediation analysis was performed using the PROCESS macro 4.1, with 1000 bootstrap iterations to decompose the total effect into direct and indirect paths. Receiver operating characteristic (ROC) curve analysis was conducted using SPSS 26.0 to evaluate the predictive performance of individual and combined biomarkers. All analyses adopted two-tailed tests, and  $p < 0.05$  was considered statistically

significant.

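### Infants already perforated when the onset sample is drawn may be counted as PNEC events that onset markers predicted

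*Combined protocol and SAP*

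**What the plan says.** Everything relevant is in the combined protocol and SAP.

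- **Entry (3.4).** The diagnosis is confirmed by clinical manifestations, pathology and "radiological evidence (pneumatosis intestinalis, portal venous gas, or pneumoperitoneum", in infants who had surgery. The three radiological signs are alternatives.
- **Predictors (3.3).** The extraction list includes "CBC parameters, lactate levels, and parameters required for calculating the nSOFA score at the onset of NEC". Onset is not defined.
- **Pneumoperitoneum as data (3.3).** It is recorded among "clinical manifestations (abdominal distension, bloody stools, pneumoperitoneum", with no date or time.
- **Outcome (3.6).** The first primary outcome is "Occurrence of perforated necrotizing enterocolitis (PNEC", with no definition, time origin or window. The second is in-hospital mortality.
- **Exclusions (3.5).** The only one that mentions perforation is "Congenital gastrointestinal malformations (e.g., intestinal atresia, Hirschsprung's disease) or spontaneous intestinal perforation". It does not cover NEC that has already perforated.
- **Purpose and analysis (2 and 3.7).** The study aims to "identify indicators that may predict the progression of neonatal NEC and its associated mortality". ROC curves are used "to evaluate the predictive performance of individual and combined biomarkers".

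**The concern.** Predicting progression to perforation only makes sense for an infant who has not yet perforated. An infant who has perforated by the time the onset blood is drawn cannot progress to that outcome, yet nothing in the plan keeps this infant out of the PNEC event count. A marker value measured alongside an existing perforation would then be scored as a successful forecast.

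This concerns who is at risk as well as when the markers are measured. A sample drawn exactly at onset does not solve the problem in an infant whose perforation is already present.

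At stake is the claim in section 1.1 and section 2 that the markers could identify high-risk infants early. An AUC that mixes existing with later perforation answers a different question, and the data as specified could not separate the two, because neither the perforation nor the sample is dated.

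**Working it through.** **Figures in the plan.** The plan gives no AUC, no PNEC proportion and no share already perforated at onset, so there is no figure to reproduce. The 220 in section 3.2 is a case count without a derivation.

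**Can such an infant be in the analysis?**

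1. Free air can contribute to the qualifying diagnosis (3.4), so entry is open to a perforated infant.
2. The exclusion in 3.5 names spontaneous intestinal perforation, a condition listed apart from NEC. It leaves perforated NEC in.
3. PNEC is counted as an occurrence with no starting point (3.6), so perforation at or before the sample counts like perforation after it.
4. No section dates the perforation, requires sampling before it, or plans a landmark or sensitivity analysis.

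The plan as written would therefore count any infant perforated by the time of sampling as a PNEC event. It does not show how many there are.

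**What would pooling do to the AUC?** The AUC is the probability that a randomly chosen case has a higher marker value than a randomly chosen control. Let *f* be the share of PNEC cases already perforated at the sample, *A0* the AUC for those cases and *A1* the AUC for later perforation, both against the same non-perforated infants. Then:

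- pooled AUC = *f* × *A0* + (1 − *f*) × *A1*
- excess over the predictive AUC = *f* × (*A0* − *A1*)

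All inputs below are assumptions. In the first two rows, AUC = Φ(d/√2): d = 1.2 gives 0.802, d = 0.3 gives 0.584 and d = 0 gives 0.50.

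| Assumed A0 | Assumed A1 | f = 25% | f = 50% | f = 75% |
|---|---|---|---|---|
| 0.802 | 0.584 | 0.64 | 0.69 | 0.75 |
| 0.802 | 0.50 | 0.58 | 0.65 | 0.73 |
| 0.85 | 0.60 | 0.66 | 0.725 | 0.79 |
| equal to A1 | any | A1 | A1 | A1 |

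For the first row at *f* = 50%: 0.5 × 0.802 + 0.5 × 0.584 = 0.693. The excess in that row is 0.25 × 0.218 = 0.05, 0.50 × 0.218 = 0.11 and 0.75 × 0.218 = 0.16. In the third row, a share of only 10% adds 0.10 × 0.25 = 0.025. A simulation of the third row agreed with the formula to within 0.002. In the last row pooling adds nothing.

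**What would restriction cost in events?** Assume 30% PNEC: 220 × 0.30 = 66 cases. Later PNEC is 66 × (1 − *f*), and the number at risk is 220 − 66 × *f*.

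| f | Later PNEC | Infants at risk |
|---|---|---|
| 10% | 59 | 213 |
| 25% | 50 | 204 |
| 50% | 33 | 187 |
| 75% | 16 | 170 |

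Section 3.6(2) lists 22 candidate markers (3 hepatobiliary, 10 blood-count and CRP, 6 ratios and indices, 2 metabolic, and nSOFA), so the lower rows would support very little modelling.

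**The case against.** A reader might go further and infer that infants are known to be perforated at time zero, that their high lactate or nSOFA is caused by the perforation, and that the PNEC AUC is therefore inflated. The documents do not support this.

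- **Timing.** Section 3.4 describes how the diagnosis is confirmed, including by surgery and pathology, so it may look back over the whole episode. It does not say that free air was on the first film. If onset means first clinical signs, the qualifying film may come after the sample.
- **Outcome definition.** Section 3.6 does not say that PNEC is identified by free air. In a surgical cohort it could be established at operation or by pathology.
- **Frequency.** Section 1.1 says that radiographic findings often appear late, but its example is pneumatosis, and the damage it mentions is not stated to be perforation. It does not show that infants perforated at onset are common.
- **Cause.** Section 1.1 links raised lactate to poor perfusion and ischaemia, which can precede perforation. A high value in a perforated infant need not result from the perforation.
- **Size.** Every AUC and share used above is assumed. If existing and later perforation are separated equally well, there is no inflation.
- **Aim.** Section 1.1 also speaks of distinguishing perforated from non-perforated disease. For that purpose, infants perforated at onset belong in the analysis.

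These points stand, and they make the problem conditional. They do not remove it. No passage keeps infants perforated by the time of sampling out of the event count, and sections 1.2, 2 and 3.7 frame the result as prediction. The undefined onset and the undated perforation are the reason the plan cannot show that the problem is small.

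**Conclusion.** The concern holds as a conditional one. The plan allows infants perforated at or before the onset sample to count as PNEC events predicted by onset markers, and it collects nothing that would identify them. If the markers separate existing perforation better than later perforation, the pooled AUC overstates their value for predicting progression by *f* × (*A0* − *A1*). Under the assumed AUCs of 0.80 and 0.58, that is about 0.05 to 0.16 for shares of 25% to 75%. The true share and both AUCs are unknown, and the excess could be nil.

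In-hospital mortality is not affected in this way, because death still follows the onset sample. One of two primary outcomes is touched, by an amount the documents do not allow anyone to estimate, so this should be fixed but is not a fatal defect.

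**What to change.** - **Section 3.3:** extract the date and time of the onset blood sample and of the first documented evidence of perforation, whether from imaging or operation.
- **Sections 3.6 and 3.7:** base any claim of predicting PNEC on infants with no documented perforation at or before the sample. Report the all-infant result as concurrent discrimination of perforated from non-perforated NEC. Give the number of infants in each group.
- **Limitation to state:** the dates mark when perforation was detected. An infant who perforated before the sample but was first recognised at operation will still be classed as a later event, so some misclassification remains.
- **Mortality:** keep all infants in that analysis.

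The cost is two date-and-time fields from the same records and one extra analysis set. The price in precision may be larger: fewer PNEC events, wider intervals and probably a lower AUC. If too few events remain, present the restricted analysis as a sensitivity analysis and describe the PNEC result as discrimination, not prediction.
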